In assessing the effects of susceptibility factors and required sample sizes in this study, we will focus on those of most clinical interest, namely alcohol, hepatitis C and UROD mutations, with estimated prevalence of 87, 69 and 20%, respectively.

Other testing. Because PCT participants typically have abnormalities in liver function tests, other causes of liver disease such as hepatitis B, diabetes mellitus, etc. will be looked for by appropriate laboratory testing as standard of care, and charged to health insurance.

- 1. Hepatitis B will be screened for by HBsAg testing.
- Fatty liver disease will be screened for by hepatic ultrasound, if clinically indicated, recognizing that increased echogenicity is consistent with but not specific for hepatic steatosis and lacks sensitivity.
- 3. Liver biopsy will be recommended, if clinically indicated.
- 4. Conditions sometimes associated with PCT, such as end stage renal disease and myelofibrosis or other bone marrow disorders impairing erythropoiesis, will be screened for as reasons for selecting therapy.

Additional testing will be done, unless results are already available from within the previous month, to include complete blood counts, serum ferritin, iron, iron binding capacity, transferrin percent saturation and a screening chemistry panel (to include sodium, potassium, chloride, carbon dioxide, blood urea nitrogen, creatinine, total protein, albumin, total bilirubin, glutamic oxaloacetic transaminase [aspartate aminotransferase], serum glutamic pyruvic transaminase [alanine aminotransferase], glucose, uric acid, calcium, and phosphorous).

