During the course of treatment by phlebotomy, samples for measuring serum ferritin and plasma total porphyrins will be obtained at baseline and at intervals of 2 weeks, or as needed to document achieving the target serum ferritin of \leq 20 ng/mL. Documenting a serum ferritin of \leq 25 ng/mL on the same day as the last phlebotomy will satisfy this requirement. Ferritin levels may not be needed every 2 weeks early in the course of treatment, but should be measured most frequently (biweekly) once the ferritin falls below 60 ng/mL and is approaching the target value of \leq 20 ng/mL.

Samples for tests such as blood counts and serum chemistries will be obtained at baseline, during the treatment phase of the study only when clinically indicated, during the post treatment phase when clinically indicated, and at the end of the follow up phase. This is the standard approach to the treatment of PCT by repeated phlebotomy in the U.S. and other countries.

It is best if therapeutic phlebotomies can be done at a site that can also send blood samples for ferritin, plasma porphyrins, blood counts and chemistries and urine porphyrins, when needed. Otherwise, additional visits will need to be arranged for monitoring these test results.

Phlebotomies will be discontinued once the target serum ferritin (\leq 20 ng/mL) is reached, which is before porphyrin levels and patterns normalize. The ferritin level should be repeated 2 weeks after the last phlebotomy, unless a ferritin of \leq 25 ng/mL was documented on the same day as the last phlebotomy. Porphyrin levels will continue to be monitored after phlebotomies have been discontinued in order to document times to each treatment outcome.

Most facilities that do phlebotomies require that a consult request or orders be provided. Suggested wording for such requests is as follows, which will need to be modified for each site and permitted hematocrit (or hemoglobin) values specified for each participant:

Please start repeated phlebotomies at intervals of approximately 2 weeks for treatment of porphyria cutanea tarda (PCT). The treatment target is a serum ferritin from the previous visit of less than 25 ng/mL.

- 1. Please call the patient to schedule the first visit.
- 2. At each visit, please
 - a. obtain an hematocrit
 - b. send a blood sample to Clinical Chemistry for serum ferritin and
 - c. obtain a blood sample for total plasma porphyrins (green top tube call extension xxxx for pickup).

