| Follow Up Lab tests- Hepatic Function Panel with reflex to PT and aPTT if abnormal, HCV RNA if positive at baseline | | х | х |
| Serum Ferritin [®] (follow up needed only for phlebotomy participants) | Х | х | Х |
| Dispense HCQ or begin phlebotomies | | X | |
| HCQ twice weekly or ~biweekly phlebotomies\$ | | Х | |
| Investigator review of labs to determine next visit | | PRN | X |
| Collection of urine for research testing | Х | X | X |

[figure not shown]
#Plasma porphyrin scan at neutral pH can be done at UTMB or ARUP, urine and plasma porphyrin measurements can be done at UTMB, ARUP, Mayo, Quest or LabCorp. During treatment phase once plasma levels drop to less than ~5 mcg/dL the test should be repeated biweekly

@ Serum ferritin should be done biweekly once the level drops below 60 ng/mL, until the target of ≤20 ng/mL is reached

[%]Complete Metabolic Panel should include- sodium, potassium, chloride, carbon dioxide, blood urea nitrogen, creatinine, total protein, albumin, total bilirubin, glutamic oxaloacetic transaminase [aspartate aminotransferase], serum glutamic pyruvic transaminase [alanine aminotransferase], glucose, uric acid, calcium, and phosphorous

^{\$} For participants on HCQ the coordinator will need to complete compliance forms monthly. For participants on phlebotomy the phlebotomy visit sheet will need to completed at every phlebotomy visit

Study flow diagram:

2. Laboratory evaluations

The tests listed below are required to assess safety of treatment or detect concurrent conditions that might affect treatment indications. Examples of the latter include advanced liver disease, chronic renal disease and myelofibrosis and other bone marrow disorders. The serum pregnancy test is needed in women of child-bearing potential to exclude pregnancy, because this is a reason for exclusion at the start of the study or for stopping treatment during the study.

- a. The following will be measured by the hospital clinical laboratory.
 - i) Tests done at baseline
 - Erythrocyte glucose-6-phosphate dehydrogenase activity

- Prothrombin time
- Partial thromboplastin time
- Total protein
- Albumin
- Total bilirubin
- Aspartate aminotransferase (glutamic oxaloacetic transaminase)
- Alanine aminotransferase (glutamic pyruvic transaminase)
- Iron
- Iron binding capacity
- Transferrin percent saturation
- Ferritin

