- Complete blood cell count (to include hemoglobin, hematocrit, red blood cell count, red blood cell indices, white blood cell count, differential white blood cell count and platelet count)

- Sodium
- Potassium
- Chloride
- Carbon dioxide
- Blood urea nitrogen
- Creatinine
- Glucose
- ii) Tests done at subsequent visits
 - Repeat baseline tests that were abnormal, or are clinically indicated
 - Total bilirubin
 - Aspartate aminotransferase (glutamic oxaloacetic transaminase)
 - Alanine aminotransferase (glutamic pyruvic transaminase)
 - Iron
 - Iron binding capacity
 - Transferrin percent saturation
 - Ferritin
 - Prothrombin time and partial thromboplastin time if liver function tests are abnormal

A urine or serum pregnancy test will be done at baseline and every 2 months until the end of treatment in premenopausal females; pregnancy is a reason for exclusion at any time during the study.

Hydroxychloroquine will be discontinued if there is worsening of liver disease, as determined by a rise in alanine aminotransferase to >300 U/L, or a two-fold increase from baseline in either total bilirubin or prothrombin time. Participants will also be monitored at each visit for signs or symptoms of worsening liver disease. Phlebotomy will be discontinued if participants are unable to tolerate this treatment at least monthly. Randomized patients discontinued from either treatment may be treated with the alternative method, since an objective of this pragmatic study is to achieve remission in all patients.

3. Ophthalmologic examinations will be done in all participants treated with hydroxychloroquine at the beginning and end of treatment. This is consistent with the recommendations of the American Academy of Ophthalmology as updated in 2011 (Table 7) [78]. Because retinal damage from 4-aminoquinolines is very rare (especially with hydroxychloroquine), it is not expected that ocular effects will be observed in this small study

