A total of at least 100 participants will be assigned, based on medical criteria, preference, or (if eligible for both treatments) by randomization, to one of these standard treatment groups. CRFs will be completed for each patient, including porphyrin levels, and data entered into the study database. This database is designed by and housed at the Data Management and Coordinating Center (DMCC) at the University of South Florida in Tampa. The DMCC is supported by the NIH Rare Diseases Clinical Research Network and serves as the secure repository for de-identified data for all consortia in the Network. Upon approval from the UTMB IRB and the Porphyrias Consortium DSMB, data from patients previously enrolled in this study at UTMB starting in 2006 before the study was a RDCRN study will be entered into the database. Subjects will be contacted to give their consent for this data transfer to the DMCC and storage in a federal data repository. For subjects who are now deceased consent will be obtained from next of kin. For subjects who cannot be re-contacted or where the next of kin cannot be re-contacted, approval of the UTMB IRB and the Porphyrias Consortium DSMB will be sought for this data transfer. Transferring this previously collected de-identified data is not expected to cause any increased risks to subjects. Data will be verified and edited where necessary for completeness and consistency by comparison with source documents. Study outcomes, such as time to achieving biochemical endpoints, will be determined from this data. As was found in the interim analysis, assignment to the two groups is unlikely to be equal, and more will be assigned to phlebotomy than to hydroxychloroquine. As in the interim analysis, times to achieving measures of remission are not expected to be substantially different for the two treatment groups. Effects of multiple susceptibility factors and other clinical and demographic features on treatment response and durability will be further examined. Outcome measures such as time to remission will be compared using Cox proportional models to study the effects of susceptibility factors on the hazard ratio to compare the two treatments. All patients who start treatment will be included in the analysis. Safety measures will be compared more descriptively where the adverse effects of each type of treatment are different.

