5. PROTECTION OF HUMAN SUBJECTS

This clinical trial will be conducted in accordance with the ethical principles that have their origin in the Declaration of Helsinki, and that are consistent with Good Clinical Practice and all applicable regulatory requirements.

5.A. RISKS TO THE SUBJECTS

Human Subjects Involvement and Characteristics. The study will enroll up to 100 subjects age 18 or greater, including nonpregnant females, with well-documented PCT selected as described above. Criteria for inclusion and exclusion are listed above in Research Design and Methods.

Sources of Materials. Research material will be laboratory information collected before and during treatment, as detailed under Methods. While samples of blood, urine and feces are ordinarily collected for clinical purposes in PCT, the number and frequency of urine and blood samples in this study will exceed somewhat those usually obtained.

Potential Risks. The study involves physical risks. *Risks from phlebotomy* and venipuncture include pain, bruising, infection, and syncope. There is a risk of iron deficiency, which may cause mild symptoms in the absence of anemia. *Risks from hydroxychloroquine*, which are generally seen with use of higher doses than in this study, include side effects such as nervousness, nightmares and other psychiatric changes, headaches, dizziness, muscle weakness, blurred vision, other visual disturbances, nausea, vomiting, diarrhea, abdominal pain and hematological changes. Chloroquine (and presumably hydroxychloroquine) overdose is especially dangerous in children. Hydroxychloroquine poses a risk of retinal damage to the fetus, and phlebotomy might impair iron status in both the fetus and the mother, so pregnancy is a contraindication for entry into the study. Specifically in PCT patients, low-dose hydroxychloroquine can result in transient increases in photosensitivity and slight increases in liver function tests and porphyrin levels. These are normal and expected in PCT patients being treated with hydroxychloroquine.

There is also risk of loss of confidentiality. These risks are not greatly increased compared to those involved in standard treatment of PCT.

5.B. ADEQUACY OF PROTECTION AGAINST RISKS

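### Section 4.F takes serum chemistries by clinical indication in the phlebotomy group, while the Schedule of Events, 4.L and 4.I list liver tests for everyone, so the descriptive safety comparison could rest on unequal testing

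*Combined protocol and SAP*

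**What the plan says.** Section 4.F, under Group 2 (phlebotomy), states that "serum chemistries will be obtained at baseline, during the treatment phase of the study only when clinically indicated". It repeats the clinical-indication limit for the post-treatment phase and adds a draw at the end of follow-up. The paragraph is specific to this arm, since it closes with "This is the standard approach to the treatment of PCT by repeated phlebotomy in the U.S. and other countries".

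Section 4.E (Other testing) defines "a screening chemistry panel (to include sodium, potassium, chloride, carbon dioxide, blood urea nitrogen, creatinine, total protein, albumin, total bilirubin", and the list goes on to AST and ALT.

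Three other places list liver tests without naming an arm:
- The Schedule of Events marks "Follow Up Lab tests- Hepatic Function Panel with reflex to PT and aPTT if abnormal, HCV RNA if positive at baseline" for both the Treatment and Follow Up periods.
- Section 4.L, item 2, describes its tests as required for assessing safety and puts total bilirubin, AST and ALT under "Tests done at subsequent visits".
- Section 4.I includes liver function tests in the follow-up visits every 3-6 months.

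The synopsis lists tolerability and safety of both treatments among the outcome measures. Section 4.R says: "Safety measures will be compared more descriptively where the adverse effects of each type of treatment are different".

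**The concern.** Liver tests are a laboratory safety measure on which the arms are expected to differ. Sections 5.A and 5.H.3 anticipate slight, transient rises on hydroxychloroquine; 5.A says "These are normal and expected in PCT patients being treated with hydroxychloroquine". Section 4.E says participants typically have abnormal liver tests before treatment, and Table 2 gives a 69% prevalence of hepatitis C in the earlier series. Values can therefore be expected to move in both arms without any drug effect.

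If one arm is tested by schedule and the other by indication, more of that movement is seen in the first arm. A side-by-side summary would then show a difference that comes partly from how often each arm was looked at. This bears on the listed safety outcome, on the hypothesis in 1.B that hydroxychloroquine works as safely as phlebotomy, and on the laboratory safety data that the DSMB reviews every 6 months (5.H).

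**Working it through.** The plan states no number of liver panels, so there is no figure to reproduce. The check is a comparison of texts, followed by a count.

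**1. Is the Schedule silent on arm by intention?** It names an arm where it wants one: the eye examination is for hydroxychloroquine participants only, and follow-up ferritin is for phlebotomy participants only. The hepatic panel row has no such limit, so on its face it covers both arms.

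**2. Does the 'clinically indicated' wording in 4.L remove the conflict?** No. That bullet concerns repeating baseline tests. Bilirubin, AST and ALT stand as separate bullets.

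**3. Could a site plausibly work from 4.F?** Yes. Phlebotomies may be done at blood banks or outside clinics. The legible part of the model order in 4.F lists hematocrit, ferritin and plasma porphyrins at each visit, with no liver tests; the text after those items was not available to check. For hydroxychloroquine, the discontinuation rule in 4.L depends on ALT, bilirubin and prothrombin time, which gives sites a reason to test that arm regularly.

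**4. Scheduled panels during about 12 months (52.18 weeks).** Inputs: visits every 2-4 weeks until plasma porphyrin is normal, then every 4-8 weeks (Schedule of Events); 6-7 months to that outcome and about 12 months to the others (4.J). Assumption: one panel at each visit, whole intervals only.

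| Time to normal plasma porphyrin | Intervals | Count |
|---|---|---|
| 6 months (26.09 weeks) | 4 then 8 weeks | 26.09/4 → 6; 26.09/8 → 3; total 9 |
| 6 months | 2 then 4 weeks | 26.09/2 → 13; 26.09/4 → 6; total 19 |
| 7 months (30.44 weeks) | 4 then 8 weeks | 30.44/4 → 7; 21.74/8 → 2; total 9 |
| 7 months | 2 then 4 weeks | 30.44/2 → 15; 21.74/4 → 5; total 20 |

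The Schedule gives about 9 to 20 panels per participant. Section 4.F guarantees 0 on treatment in the phlebotomy group.

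**5. Follow-up.** Section 4.J expects at least 3 years. At 3-6 month visits, 4.I gives 36/6 = 6 to 36/3 = 12 sets of liver tests. Section 4.F guarantees one, at the end.

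**6. What unequal ascertainment can do (illustration; the rates are assumptions).** Let the true proportion with a liver-test rise be p in both arms, with all rises seen on hydroxychloroquine and a fraction f seen on phlebotomy. The observed proportions are p and p × f, and the spurious gap is p × (1 − f).
- p = 20%, f = 0.5: 20% against 10%. With 50 per group (the figure in 4.R), that is 10 participants against 5.
- p = 20%, f = 0.25: 20% against 5%.
- Over p = 10-30% and f = 0.25-0.75, the gap runs from 10% × 0.25 = 2.5 to 30% × 0.75 = 22.5 percentage points.

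**The case against.** The strongest reply is that the texts can be read consistently. The Schedule has two laboratory rows: screening tests (metabolic panel, blood count) at baseline only, and a hepatic function panel during treatment and follow-up. The 4.F sentence, about blood counts and serum chemistries, resembles the first row and never names the hepatic panel. This reading is possible, but the plan does not state it, and bilirubin, AST and ALT belong to the metabolic panel by its own footnote. The ambiguity remains.

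Second, no liver comparison is specified. Section 4.B says that comparing safety is not an objective, 5.H puts the emphasis on time to remission, and Aim 1 assesses safety by interviews and questionnaires. This stands as a limit on importance. It does not remove the synopsis outcome or the descriptive comparison in 4.R.

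Third, equal sampling would not by itself give a clean comparator. Table 3 bars hydroxychloroquine for ALT above 200 U/L, bilirubin above 3 mg/dL, continued heavy alcohol use and high ferritin, so such patients go to phlebotomy, and 4.B expects most participants not to be randomized. This stands in full and shapes the remedy.

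Fourth, the visit counts are upper-end figures. Early visits may be less frequent, and some contacts are by telephone. This also stands.

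**Conclusion.** The inconsistency is real and should be corrected. Its effect is limited to the descriptive liver-safety comparison, and it arises only to the extent that sites followed 4.F. In that case the contrast is 0 guaranteed on-treatment panels on phlebotomy against about 9 to 20 on hydroxychloroquine, assuming a panel at every visit.

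Three stronger readings are not supported:
- **That the phlebotomy group has no liver data until the end of follow-up.** This would need 4.F to override the Schedule, 4.L and 4.I together. Even under 4.F there are baseline, indication-driven and end-of-follow-up values, and 4.L repeats abnormal baseline tests. The comparator would be selectively sampled, not missing.
- **That a false-flag rate can be calculated from repeated panels.** The documents give no per-panel rate, and independence is implausible for serial liver tests in one patient. The gaps shown above are likewise illustrations, not estimates.
- **That the main result is at risk.** Time to remission rests on porphyrin measurements and is unaffected.

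Which testing rule is clinically right is not judged here.

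**What to change.** Reconcile the Group 2 paragraph of 4.F with the Schedule of Events, 4.L and 4.I. State the study's scheduled liver-test collection once, on the same basis for both groups, and say whether the 4.F reference to serum chemistries includes bilirubin, AST and ALT. The sponsor and investigators decide what that schedule is. Indication-driven testing stays with the investigators.

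Add to 4.R:
- Liver-test changes from baseline are summarized by arm using only time points sampled by schedule in both arms. Indication-driven values are listed separately.
- The summary notes that Table 3 directs patients with marked liver abnormalities to phlebotomy, and shows the randomized subset separately.

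The reporting rule also applies to participants already enrolled. Where a site followed 4.F, the common scheduled points may be only baseline and end of follow-up, and the report should say so. The randomized subset will be small: fewer than half were randomized in the interim analysis, which at 100 participants would mean fewer than 50 across both arms.

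The cost is a short protocol clarification and a few lines in the analysis section. Most of the assays are already in the Schedule, but some added assays or visits will be needed where the phlebotomy facility cannot send chemistries, as 4.F acknowledges.

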Change of treatment. Treatment may need to be changed due to incomplete response or to side effects or intolerance of the initial treatment. Change of treatment will be a clinical decision by the investigator and the patient, and the reasons will be recorded on the CRFs. The second treatment will be monitored as part of the study with an additional set of the treatment-related CRFs in the same manner as the first treatment. Data collected after a change in treatment will be analyzed descriptively and separately from data collected during the first treatment.

Treatment of recurrences. Patients will be followed after completion of treatment in order to determine the frequency of recurrent disease, as indicated by increases in porphyrin levels with or without recurrent cutaneous manifestations. These recurrences will be monitored as part of the study. Data collected during treatment of recurrences will be analyzed descriptively and separately from data collected during the first treatment. These provisions will provide information about all treatment that is needed for this disease, since repeated courses of treatment greatly increase the impact of the disease.

4.G. Study visits during the Treatment Phase. During the Treatment Phase, participants will be scheduled to return to the study site or be contacted by the study site by telephone at 2 week intervals. A study visit can be scheduled after longer than 2 weeks based on careful review of data from the last visit. If this is contemplated, the investigative team should evaluate clinical features and laboratory results within 1 week, to be sure that a longer visit interval will not impair

capturing timely data within a documentation window. Sometimes study information can be collected by telephone, including recording of patient-reported skin manifestations, and by special arrangements study samples collected locally and shipped to the study site.

The treatment outcomes for this study are documentation of times to normalization of several porphyrin laboratory measurements, which occur in sequence at different times during the Treatment Phase. Study performance will be assessed by whether or not primary study outcomes are documented within specified time windows. *Documenting the time to each outcome requires an abnormal result followed by a normal result within a specified time window.* The windows of documentation for each treatment outcome are shown in Table 5. Experience to date indicates that these outcomes are usually achieved in the order shown. All outcome measures may not be documented in all patients, but with four rather than one outcome measure it is more likely that each patient will achieve documentation of at least some of these outcomes.

| Table 5. Treatment outcomes and windows for documentation | | |
|---|------------------|--|
| Treatment Outcomes | Windows for | |
| | Documentation of | |
| | Outcomes | |
| Normal plasma porphyrin level | 4 weeks | |
| Disappearance of plasma fluorescence peak | 8 weeks | |
| at ~619 nm | | |
| Normal urine total porphyrins | 8 weeks | |
| Normal pattern of urinary porphyrins | 8 weeks | |

Time to achieving each of these treatment outcomes and the location of each of these outcome windows in time during the Treatment Phase will vary among individual participants. For this reason, regular visits should be scheduled based on these windows, and less frequent visits scheduled only after examination of the most recent laboratory results.

4.H. End of treatment. The maximum duration of treatment will be 24 months, but is expected to be shorter for most participants. Treatment by phlebotomy will end when the target ferritin value is reached (≤20 ng/mL, or ≤25 ng/mL on the day of the last phlebotomy). Therefore, it is advantageous, if possible, to obtain ferritin measurements on the days of phlebotomy. Porphyrin levels will start to decrease, but will not be normal when phlebotomies are ended. Therefore the Treatment Phase of the study extends beyond the last phlebotomy until all treatment outcomes are documented. Factors that may lengthen the duration of phlebotomy treatment include marked iron overload, some loss of venous access and difficulty adhering to treatment visits.

Hydroxychloroquine treatment will end after the plasma total porphyrin concentration and other porphyrin abnormalities have been normal for at least one month (i.e. at least one month after all treatment outcomes are achieved). Treatment may be stopped for poor tolerance or other medical reasons, and these reasons will be recorded. For hydroxychloroquine, the desirable length of this treatment and factors that delay response are less well understood, and will be clarified by the results of this study. For this protocol, the duration of hydroxychloroquine treatment will not exceed 24 months.

Either treatment will be discontinued if a participant no longer meets the inclusion criteria or develops one of the exclusion criteria for the assigned treatment. A treatment will also be stopped if an adverse event occurs that is regarded as a reason for stopping the current

treatment or in the judgment of the investigators on clinical grounds is a reason for stopping the current treatment in the best interest of the patient. The reasons for discontinuing treatment will be recorded on the CRFs. If a participant is discontinued from one treatment, they may be switched to the alternate treatment if deemed appropriate by the investigator. Should this happen their information will still be collected according to the schedule described in this protocol and analyzed as part of this study.

4.I. Follow Up Phase. Determining durability of treatment after achieving a complete biochemical remission of PCT is an important objective of this study. Therefore, subjects will be observed long term during the Follow Up Phase for clinical and biochemical recurrences of PCT. This phase will begin after treatment is completed and all treatment outcomes are achieved. These visits will occur, either on site or remotely, every 3-6 months for up to 5 years, or possibly longer, depending on the availability of funding for the study. Symptoms will be monitored, and porphyrin levels measured for early detection of recurrence. Determinations on these visits will include total plasma and urinary porphyrin concentrations, plasma porphyrin neutral pH fluorescence emission peak, urinary porphyrin HPLC, ferritin and liver function tests. These samples may be obtained at the study site or elsewhere as part of standard of care. This will provide information on both clinical and subclinical biochemical recurrence after remission with both types of treatment. If a subject has a recurrence of symptoms their treatment will be followed clinically and they will continue with this follow up visit schedule.

It is important to assess both symptoms and porphyrin levels during follow up. In our experience patient reports of recurrence of skin manifestations are not always reliable, and can be discounted if evaluation at the time finds that porphyrin levels remain normal and no objective skin changes consistent with PCT are present. Conversely, biochemical recurrence with small or large increases in porphyrins can occur in the absence of symptoms. It is suspected that subclinical PCT may be especially common in patients with *UROD* mutations, but this is not well documented.

- **4.J. Study duration and end of study.** The duration of the study including the Follow Up Phase is at least five years. It is possible that the study will be extended further depending on results and the availability of funding. Subjects will enter the study needing treatment, and require up to 24 months of treatment and observation to document achieving the treatment outcomes, followed by at least 3 years of follow-up. Therefore, the most frequent study visits will occur during the Treatment Phase and generally the first ~12 months of the study, which includes active treatment and the treatment outcome windows to document biochemical remission. Based on the interim analysis (45) it is anticipated that the first outcome (a normal plasma porphyrin concentration) will be reached within 6-7 months, on average. Other treatment outcomes should be achieved within ~12 months, although this is uncertain at present, since such observations were not part of the interim analysis.
- **4.K. Treatment outcomes and schedule of events.** A schedule of events in tabular form and a study flow diagram are shown below. This study compares time to reaching certain efficacy outcomes with the two treatments and documents durability of treatment in terms of absence of increases in porphyrins and recurrence of symptoms.

The primary efficacy outcome is achieving a normal plasma porphyrin concentration (<0.9 mcg/mL). Secondary efficacy outcomes include achieving (1) absence of a fluorescence peak in diluted plasma at neutral pH; (2) a normal level of total urinary porphyrins; (3) a normal pattern of individual porphyrins in urine (defined as total highly carboxylated porphyrins less than coproporphyrin); (4) times to achieving intermediate improvements in these porphyrin

measures, which will be defined during data analysis; (5) absence of new skin lesions for at least 3 months; and (6) effects of susceptibility factors such as hepatitis C, inherited UROD deficiency, etc. on achieving these treatment outcomes.

Durability of treatment (i.e. absence of recurrence) is recorded as beginning with the time that treatment achieves the treatment outcomes, and extends to the time of repeat documentation of a normal plasma porphyrin concentration, assuming there have been no interim recurrences of skin manifestations.

4.L. Safety. Safety parameters are based on known side effects of both treatments and include suggestions of the UTMB IRB and the FDA CDER. Participants will be evaluated at the beginning of the study to ensure that they meet the entry criteria and are informed about risks and precautions. They will then be monitored at study visits for assessment of safety. Close monitoring of hemoglobin or hematocrit may occur as a part of standard treatment by phlebotomy. This is not the case for hydroxychloroquine, because initiation of treatment in clinical practice requires only one visit to prescribe the drug, and continued visits are not needed to administer treatment. Therefore, safety monitoring will be as good or better than in clinical practice.

1. History and physical examination

History and physical examination (including height and weight) will be performed at the beginning and end of the study. Results will be recorded on CRFs.

Schedule of Events

| | Baseline (Day -60 to Day -1) | Treatment Period (including all treatment outcomes) | Follow Up Period (to monitor for recurrence) |
|---|------------------------------------|---|--|
| Visit frequency | One visit or as needed | Every 2-4 weeks until plasma porphyrin concentration normal, then every 4-8 weeks | Every 3-6 months |
| Medical History and physical examination | Х | | Annually & End of study |
| Documentation of PCT & porphyrin testing- urine total porphyrins, plasma total porphyrins*, erythrocyte protoporphyrin, UROD mutation testing, erythrocyte UROD, urine ALA & PBG, fecal porphyrins (optional) | х | | |
| Lab assessment for susceptibility factors- serum anti- HCV (with follow up HCV RNA if positive), serum anti- HIV, HFE mutation testing | X | | |
| Screening Lab tests- serum ferritin, complete metabolic panel%, CBC with Diff, hemoglobin A1C, Erythrocyte glucose-6-phosphate dehydrogenase screening, PT, aPTT, serum iron & TIBC | Х | | |
| Alcohol & Tobacco Use Questionnaires | X | | |
| History of Estrogen Use (type, dose, duration, how recent) | Х | | |
| PCT Symptom Assessment | Х | Х | Х |

| Liver ultrasound and/or liver biopsy (if clinically indicated) | Х | | |
|---|---|----------|---|
| Ophthalmologic Evaluation (only for HCQ participants) | Х | Annually | |
| Plasma and urine (24 hour or spot sample) total porphyrins, quantified & plasma porphyrins fluorescent peak# | | X | X |
| Urine pregnancy test | Х | X | |
| Follow Up Lab tests- Hepatic Function Panel with reflex to PT and aPTT if abnormal, HCV RNA if positive at baseline | | х | х |
| Serum Ferritin [®] (follow up needed only for phlebotomy participants) | Х | х | Х |
| Dispense HCQ or begin phlebotomies | | X | |
| HCQ twice weekly or ~biweekly phlebotomies\$ | | Х | |
| Investigator review of labs to determine next visit | | PRN | X |
| Collection of urine for research testing | Х | X | X |

[figure not shown]
#Plasma porphyrin scan at neutral pH can be done at UTMB or ARUP, urine and plasma porphyrin measurements can be done at UTMB, ARUP, Mayo, Quest or LabCorp. During treatment phase once plasma levels drop to less than ~5 mcg/dL the test should be repeated biweekly

@ Serum ferritin should be done biweekly once the level drops below 60 ng/mL, until the target of ≤20 ng/mL is reached

[%]Complete Metabolic Panel should include- sodium, potassium, chloride, carbon dioxide, blood urea nitrogen, creatinine, total protein, albumin, total bilirubin, glutamic oxaloacetic transaminase [aspartate aminotransferase], serum glutamic pyruvic transaminase [alanine aminotransferase], glucose, uric acid, calcium, and phosphorous

^{\$} For participants on HCQ the coordinator will need to complete compliance forms monthly. For participants on phlebotomy the phlebotomy visit sheet will need to completed at every phlebotomy visit

Study flow diagram:

2. Laboratory evaluations

The tests listed below are required to assess safety of treatment or detect concurrent conditions that might affect treatment indications. Examples of the latter include advanced liver disease, chronic renal disease and myelofibrosis and other bone marrow disorders. The serum pregnancy test is needed in women of child-bearing potential to exclude pregnancy, because this is a reason for exclusion at the start of the study or for stopping treatment during the study.

- a. The following will be measured by the hospital clinical laboratory.
 - i) Tests done at baseline
 - Erythrocyte glucose-6-phosphate dehydrogenase activity

- Prothrombin time
- Partial thromboplastin time
- Total protein
- Albumin
- Total bilirubin
- Aspartate aminotransferase (glutamic oxaloacetic transaminase)
- Alanine aminotransferase (glutamic pyruvic transaminase)
- Iron
- Iron binding capacity
- Transferrin percent saturation
- Ferritin
- Complete blood cell count (to include hemoglobin, hematocrit, red blood cell count, red blood cell indices, white blood cell count, differential white blood cell count and platelet count)

- Sodium
- Potassium
- Chloride
- Carbon dioxide
- Blood urea nitrogen
- Creatinine
- Glucose
- ii) Tests done at subsequent visits
 - Repeat baseline tests that were abnormal, or are clinically indicated
 - Total bilirubin
 - Aspartate aminotransferase (glutamic oxaloacetic transaminase)
 - Alanine aminotransferase (glutamic pyruvic transaminase)
 - Iron
 - Iron binding capacity
 - Transferrin percent saturation
 - Ferritin
 - Prothrombin time and partial thromboplastin time if liver function tests are abnormal

A urine or serum pregnancy test will be done at baseline and every 2 months until the end of treatment in premenopausal females; pregnancy is a reason for exclusion at any time during the study.

Hydroxychloroquine will be discontinued if there is worsening of liver disease, as determined by a rise in alanine aminotransferase to >300 U/L, or a two-fold increase from baseline in either total bilirubin or prothrombin time. Participants will also be monitored at each visit for signs or symptoms of worsening liver disease. Phlebotomy will be discontinued if participants are unable to tolerate this treatment at least monthly. Randomized patients discontinued from either treatment may be treated with the alternative method, since an objective of this pragmatic study is to achieve remission in all patients.

3. Ophthalmologic examinations will be done in all participants treated with hydroxychloroquine at the beginning and end of treatment. This is consistent with the recommendations of the American Academy of Ophthalmology as updated in 2011 (Table 7) [78]. Because retinal damage from 4-aminoquinolines is very rare (especially with hydroxychloroquine), it is not expected that ocular effects will be observed in this small study

